## OBJECTIVES AND HYPOTHESES

At present no published clinical trial has reported the use of video-based interventions to improve HIV treatment related patient outcomes in low-resource countries. The proposed research addresses a question critical to optimize PMTCT service delivery and will also provide needed data regarding the impact of inexpensive, scalable video-based interventions in the field of HIV prevention and treatment. Our specific aims and hypotheses are:

**Specific aim 1: To evaluate the effectiveness of VITAL start on improving partner outcomes (disclosure, testing, and linkage to ART), maternal retention and ART adherence via a multi-site, parallel group (n=446 each group), randomized controlled, outcome assessor blinded trial.**  
We hypothesize that: the proportion of partners who are disclosed to, receive HIV testing, and are linked to ART will be higher in the intervention vs. control group at 3 months follow-up and; the proportion of women retained in care (**primary outcome**) and adherent to ART (self report, and undetectable viral load) at 12 months after ART initiation will be higher in the intervention vs. control group.

[figure not shown]
**Specific aim 2: To critically examine the delivery of VITAL start** via in-depth interviews and surveys administered to patients, partners, and health workers. Adoption of and satisfaction with the program will be measured. Qualitative interviews will be utilized to obtain feedback on motivational qualities of the program and benefits and challenges of delivery.

**Specific aim 3: To assess the cost-effectiveness of the VITAL start intervention.** Cost-effectiveness will be assessed using incremental cost-effectiveness ratios, with health effects expressed in terms of viral load suppression and costs of resources used for the intervention.

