## Data analysis plan:

The intent to treat (ITT) population is defined as all randomized subjects, regardless of when they withdrew from the study. We will exclude the ineligible patients and thus perform modified ITT analysis as the primary analysis to facilitate interpretation if the exclusions do not disrupt the baseline equivalence established by random assignment and bias the results. We also include who completed the intervention, and with follow up data to conduct secondary and exploratory analyses of the secondary efficacy data and explorative outcomes, for example viral load, which is only available at month 6 and 12. There is no planned interim analysis for this study. All hypothesis testing will be

carried out at the 5% (2-sided) significance level unless otherwise specified. Additional ad-hoc analyses may be conducted as deemed appropriate and any changes, including the rationale for use will be documented in the clinical study report. All statistical analysis will be performed using SAS® v9.4, R 4.2.2, Stata 17 or higher for Windows.

Demography and baseline characteristics include age, socioeconomic, pregnancy and HIV variables. etc Descriptive statistics, such as, mean, standard deviation (SD) for continuous variables, and frequency and proportion for categorical variables, will be calculated by treatment group. Baseline differences will be compared using two-tailed independent t-tests (means) and chi-square tests (%) to evaluate the balance of patient characteristics in two groups by the randomization.

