The primary efficacy endpoint is the composite outcome of achievement of retention and viral suppression at Month 12. The primary efficacy endpoint will be analyzed using a binary goal attainment variable (is the achievement of retention and viral suppression [1 yes/0 no]). Participants will be considered retained in care if they are verified by clinic records as active on ART. Retention (1 Yes) will be defined as alive and attending ART clinic, as per clinic verified records, within specified window of the follow up visits. All else without known status or retention information (Due to stopped, LTFU/defaulted, transferred out, missed appointment, and missing) will be defined as Retention (0 No). Amongst those retained the study will then assess viral suppression which will be measured as viral load less than 1,000 copies per milliliter. A sensitivity analysis using detectable vs. undetectable viral load will be performed. Missing viral load information will be treated as not suppressed. There is no missing data on the primary outcome by definition.

The number and proportion of subjects who achieved retention and viral suppression at Month 12 will be summarized by treatment group. The comparison of the proportion of success in the two treatment groups will be conducted using Chi-square tests followed by logistic regression including treatment, center, and other baseline prognostic factors. Important baseline prognostic factors of the main outcome (p-values < 0.2 from univariate analysis) will be entered into the model. The main exposure variable and any factors, such as age, prior history of ART, deemed to be clinically relevant will be forced into the model regardless of the statistical significance. A backwards selection procedure will be performed to select other factors. Variables achieving statistical significance will be retained in the model. Covariates will be checked for collinearity using the variance inflation factor. Where collinearity occurs between two variables, only one of these variables will be included in the final model. An assessment of the model goodness-of-fit will be performed using the Hosmer-Lemeshow test, deviance test, and visual inspection of index plots. The adjusted odds ratio of achieving retention and adherence at Month 12 on VITAL Start versus Control will be reported along with the 95% confidence interval and 2-sided p-value.

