Secondary efficacy outcomes include achievement of retention and viral load suppression at month 6, retention at month 12, viral suppression at month 12, TFV-DP and 3TC adherence status at month 12 (for selected subcohort), and self-reported adherence status at month 12. The statistical method detailed above will be applied.

Other explorative measures include knowledge inventory, patient-Provider relationship, pregnancy intention, satisfaction with the counselling, adherence-self efficacy, partner disclosure, motivation and behavior skills, perceived social support, self-Reporting Questionnaire (SRQ)- Mental health assessment (depression and anxiety), adverse Childhood Events – International Questionnaire (ACE-IQ), cigarette use, alcohol use disorders identification test (AUDIT), drug use disorders Identification Test (DUDIT), family planning intentions, side effects, intimate partner violence (IPV), contamination measures, infant outcomes and COVID-19 impact. Descriptive statistics will be calculated for all measures and displayed by treatment group and visit as appropriate. For continuous outcomes, such as ART knowledge measures, adherence self-efficacy score, motivation and behavioral skills, perceived social support score and self-perceived patient-provider quality of HIV care score, two-

sample t-tests will be used to compare 12-month outcomes and linear mixed models will be used to examine differences in trajectories over time between the intervention and control groups. For categorical outcomes, the number and proportion of the categories at Month 12 will be compared using Chi-square tests. Generalized Estimating Equation (GEE) method for repeatedly measured categorical outcomes will be applied to compare the outcome across time between two groups while accounting for the correlation among repeated measures from the same subject.

---

**Specific aim 2: To critically examine the delivery of VITAL start** via in-depth interviews and surveys administered to patients, partners, and health workers. Adoption and satisfaction with the program will be measured. Qualitative interviews will be utilized to obtain feedback on motivational qualities of the program and benefits and challenges of delivery.

---

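### Month-12 chi-square tests and a GEE with no stated working correlation leave the categorical survey outcomes (partner disclosure, partner violence) open to bias if dropout depends on earlier outcomes and differs by arm

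*Combined protocol and SAP*

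**What the plan says.** All of this is in the combined protocol and SAP.

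- **Status.** The Data analysis plan treats these outcomes as exploratory: "Other explorative measures include knowledge inventory, patient-Provider relationship, pregnancy intention, satisfaction with the counselling, adherence-self efficacy, partner disclosure". Intimate partner violence is in the same list.
- **Month 12.** "For categorical outcomes, the number and proportion of the categories at Month 12 will be compared using Chi-square tests".
- **Over time.** "Generalized Estimating Equation (GEE) method for repeatedly measured categorical outcomes will be applied to compare the outcome across time between two groups". The sentence goes on to say that the method allows for correlation within a woman, but it names no working correlation.
- **Who is analysed.** "We also include who completed the intervention, and with follow up data to conduct secondary and exploratory analyses".
- **Missing data.** The only rule is for retention and viral suppression, where missing counts as failure: "There is no missing data on the primary outcome by definition". The survey outcomes have no equivalent rule.
- **Continuous outcomes.** Two-sample t-tests at month 12, and over time "linear mixed models will be used to examine differences in trajectories over time between the intervention and control groups".
- **Hypothesis.** Specific aim 1 expects that "the proportion of partners who are disclosed to, receive HIV testing, and are linked to ART will be higher in the intervention" group, and sets this comparison at 3 months.
- **Follow-up.** Under Follow up, survey visits are held apart from ART refills, may be done by phone, and are backed by tracing and a transport allowance.

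**The concern.** An available-case chi-square test, and a GEE with independence working correlation, compare the women who happen to be seen. That is a fair comparison of the randomised arms only if being seen is unrelated to the outcome, or is related to it in the same way in both arms.

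The trial's own premise makes this doubtful. The section on creation of the video lists fear of disclosure, above all to partners, among the barriers found in interviews that included women lost to follow-up. The Intervention Group paragraph expects the video to improve both disclosure and retention. If that is right, dropout is related to the outcome and its amount differs by arm.

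Two things are at stake. Partner disclosure is part of a stated Aim 1 hypothesis. Partner violence is named as a possible risk of the intervention in the risks section. A distorted contrast on either would mislead, even though both are labelled exploratory.

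**Working it through.** **1. What the plan gives on loss.** There is no figure for survey loss. The only attrition figure is 5%, from transfer-outs, in the Sample Size Calculation. That calculation reproduces if the control rate, which is not given, is taken as 40–45%. A 15-point difference at two-sided alpha 0.025 and 90% power needs 273 per arm; 273/0.85² = 378 for contamination; 378/0.95 = 398 for attrition; 398 × 1.12 = 446. It concerns the primary endpoint only.

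**2. Clinic loss at the three named sites (Table 1, month 12).** Kawale 176/406 = 43.3%; Mangochi 57/121 = 47.1%; Area 25 179/385 = 46.5%. Pooled: 412/912 = 45.2%. (Area 25's printed 58% retained does not match its fraction, 206/385 = 53.5%; the printed figure would mean 42% lost.) This is loss from routine ART care. Survey loss is therefore an assumption, taken here as somewhere between 5% and 45%.

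**3. Simulation with graded dropout (all inputs assumed).** Four visits; control rates 45/50/55/60%; video rates equal to control (null) or 55/60/65/70%; latent correlation 0.6. Per-visit dropout is 5–8% if the outcome was present at the last visit, 3–4 times that if absent, and multiplied by 0.6–1.0 in the video arm. Observed-case differences, which are also what an independence GEE with visit-by-arm means returns:

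| Setting | True | Observed |
|---|---|---|
| Month 12, null, 40% less dropout in video arm, 24–47% missing | 0 | −2.3 to −3.8 |
| Month 12, null, control loss about 10–14% | 0 | off by under 1 |
| Month 12, real effect, 30% less dropout in video arm | 10 | 6.3 to 8.8 |
| Month 12, real effect, same dropout rule in both arms | 10 | 9.1 to 9.6 |
| Month 3, 6–22% missing | – | off by at most 1.4 (1.7 in a second run) |

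The false difference is negative because the video arm keeps more of the women without the outcome. An unweighted GEE with exchangeable correlation stayed within about 1 point of the full-data value.

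**4. Scale against sampling error.** The 800 enrolled give about 400 per arm. Taking the ends of the 24–47% range as the two arms, 304 and 212 women are seen. At a 50% rate, SE = √[0.25 × (1/304 + 1/212)] = 4.5 points. A bias of 2 to 4 points is 0.44 to 0.89 SE. The chance of a two-sided 5% rejection under the null, Φ(−1.96 + b) + Φ(−1.96 − b), is then about 7% at b = 0.44 and 14% at b = 0.89.

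**5. Extreme case.** True null, 50% at every visit, and dropout driven by the last outcome in the control arm only.

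| Total loss | Month-12 observed, control vs video | Odds ratio, independence GEE | Odds ratio, exchangeable GEE | Chi-square rejection (400 per arm, 500 runs) |
|---|---|---|---|---|
| 5% | 0.507 vs 0.499 | 0.97 | 1.00 | 4% |
| 20% | 0.531 vs 0.500 | 0.88 | 1.00 | 12% |
| 45% | 0.584 vs 0.500 | 0.71 | 0.98 | 37% |

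Check on the last row: (0.500/0.500)/(0.584/0.416) = 0.71. Weighting by the inverse probability of being seen gives 0.506 vs 0.500 at 45% loss. When the same outcome-driven rule applies in both arms, rejection stays at 4–6% and the odds ratio at 0.97–1.00, although at 45% loss both arms' proportions are about 0.58 instead of 0.50.

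**The case against.** Several counter-arguments are sound.

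- **GEE as such is not the problem.** A reader might infer that any unweighted GEE is badly biased here. The plan says its GEE accounts for within-woman correlation, and with an exchangeable structure most of the bias disappeared. This stands, with two limits: the simulated data had a common correlation across visits, which favours that choice, and the plan does not commit to it. It does nothing for the chi-square test.
- **Clinic loss is not survey loss.** A reader might infer that over 40% of survey data will be missing. Table 1 reports routine ART retention. Phone surveys, a separate location and tracing can reach women who have left ART care.
- **The partner hypotheses are at 3 months.** A reader might carry the Month-12 bias over to Aim 1. At month 3 it was at most about 1.7 points. Partner testing and linkage are also absent from the plan's list of exploratory measures, so their analysis is not described there.
- **Continuous outcomes are not fully protected either.** Their month-12 t-tests share the available-case limitation; only the mixed model does not.
- **Unweighted and complete-case are not the plan's words.** They are inferred from its silence and from the restriction to women with follow-up data. The inference is reasonable, but it is an inference.
- **Weighting recovered the truth by construction,** because the true dropout model was used. If a woman misses a visit because of current violence or non-disclosure, weighting on past outcomes will not correct that.

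**Conclusion.** The concern holds in limited form. The planned Month-12 chi-square tests, and the GEE if run with independence working correlation, are open to bias in the arm contrast when dropout depends on earlier outcomes and differs by arm. The trial's hypotheses make that plausible; the documents do not show that it occurs.

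The size is conditional. It is a false −2 to −4 points at Month 12 only with outcome-driven dropout of three to four times, 40% less dropout in the video arm and 24–47% missing, all of them assumptions. With low loss, or one dropout rule for both arms, it was about 1 point or less in the settings run, and it grows with loss. Simulated outcome rates were near one half, so the figures should not be carried over to partner violence if that is much rarer.

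The documents do not support the stronger statements that these methods fail unless data are missing completely at random, or that survey loss will exceed 40%. The outcomes are exploratory, and the primary result has its own missing-data rule and is unaffected.

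**What to change.** For the repeated categorical survey outcomes:

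1. State the survey loss expected at each visit and the dropout mechanism assumed.
2. Take the month-3 and Month-12 arm contrasts from one model that is valid when dropout depends on observed data: GEE after multiple imputation, or inverse-probability-weighted GEE. Use arm, clinic, baseline factors and previous outcomes in the imputation or dropout model.
3. Name the working correlation.
4. Keep the chi-square tests and the unweighted GEE as sensitivity analyses.
5. Add a sensitivity analysis for dropout that depends on the unobserved current outcome, for example imputation with a range of shifts by arm.

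The cost is SAP wording and modest programming on data already being collected. The downside is slightly wider intervals and one more model to specify in advance.

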### **Suboptimal maternal retention and adherence to ART- one of the most critical challenges facing PMTCT service delivery globally**

In order to significantly reduce the number of new infant HIV infections, PMTCT retention rates in excess of 90% are required. Unfortunately, maternal retention and adherence to ART remain suboptimal. A national evaluation from Malawi demonstrated that as compared to women who initiated ART for their own health, those who started for PMTCT (B+) were five times more likely not to return to clinic [OR 5.0, 95 % confidence interval (CI) 4.2–6.1]. The most recent Malawi national B+ retention rates were 78%, 71%, and 67% at 6, 12, and 24 months, respectively. The majority of women lost to follow-up only experienced one visit—when they discovered their HIV-positive diagnosis—and it is likely that many never actually started ART. This problem is not limited to Malawi—suboptimal maternal retention and adherence is one of the most critical challenges facing PMTCT services globally. Non-adherence is a major cause of viremia that greatly increases the risk of vertical transmission. Further, viremia while on ART is the central cause of antiretroviral resistance and poor clinical outcomes. *Improving viral suppression in pregnant and post-partum women on ART will likely become one of the most important challenges to PMTCT programs globally.*

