**Figure 3: Hypothesized pathway via which VITAL start may improve partner outcomes and maternal retention and adherence**

**Control Group:** Patients randomized to the control arm will receive the usual standard of care (SOC) pre ARV initiation education with the National ARV Educational Flipchart (typically takes one hour).

**Study Duration:** We estimate enrolling all subjects within 3 years and will follow subjects until the last woman has reached 12 month follow up

**Follow up:** Participants will be asked to attend a study follow-up visit at 1 month, 3 months, 6 months and 12 months after enrollment, at a separate location and time from where they receive their ART refills to reduce confounding. Surveys may be done via phone if that is the participant's preference. At these visits, women will be asked to complete an outcome assessor-administered survey with validated tools to a brief knowledge, motivations and behaviors assessment, experience of intimate partner violence (IPV), partner HTC/sexual history, adherence self-efficacy, perceived social support, perception of received health services support, alcohol and drug use, anxiety and depression screening and ART side effects. Dried blood spots for viral load (VL) testing will be collected at 6- and 12 months. We will collect an additional dry blood spot (DBS) at the 12-month visit. There will be shipped to the University of North Carolina Clinical Pharmacology and Analytical Chemistry Laboratory at Chapel Hill, North Carolina, USA for pharmacokinetic analysis. If participants fail to attend follow-up visits, tracing will be attempted by study staff. Consistent with other studies in Malawi, a transport allowance will be provided for each study visit.

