#### **Sample Size Calculation:**

The primary outcome for this study is a composite outcome of retention in care and maternal viral suppression that has been used in similar previous studies. This outcome was selected to measure the ultimate goal of ART use within PMTCT services: to keep HIV+ mothers engaged in care and virally suppressed to maximize the benefits of ART for both treatment and prevention. This outcome assumes that those not retained are not virally suppressed. The sample size calculation is

based on a comparison of the proportions of those in the intervention versus SOC arms reaching the combined primary endpoint at 12 months after maternal ART initiation. Pearson Chi-square test for Proportion Difference was used for calculation. A combination of various scenarios was considered for retention in care (50-90%), maternal viral suppression (50-90%) among those retained, and contamination rate (0-15%). A difference of 15% was selected as the smallest difference that would be of clinical significance. It is also assumed that an effect of this magnitude could be anticipated in this field of research.

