Prospectively, we will collect information regarding costs of administering both the VITAL start and the SOC pre-ART counseling. To measure staff time devoted to pre- ART counseling, we will perform time-motion assessments in line with the STAMP (Suggested Time and Motion Procedures). We will sample sufficiently to account for potential sources of heterogeneity such as study clinic and provider. We will randomly sample provider sessions from each arm of the study and each participating study clinic during every month of participant enrolment. A minimum of 4 assessments will be conducted per clinic every month. Therefore, we anticipate collecting data on over 200 pre-ART counseling sessions. Repeat sampling of providers is expected and will be recorded. The value of staff time will then be estimated as the product of their gross salary and share of time allocated to intervention/pre ART counseling.

**Cost effectiveness analysis:** We will calculate incremental cost-effectiveness ratio (ICER), for the primary outcome of economic interest: proportion of women virally suppressed at 6 months follow up. The ICER is the difference in costs between two interventions divided by the difference in their effects, and can be interpreted as the incremental price of a unit health effect from the intervention under study, as compared to the alternative.

We will conduct one way and multi-way sensitivity analysis to model cost-effectiveness under various conditions, such as lower pricing of video production, mode of delivery, tablets, and alternate health care workers cadres to deliver the intervention. Finally, we will conduct probabilistic sensitivity analysis using bootstrapping methods to ascertain robustness of our results to extreme assumptions/scenarios. Based on emerging literature, we will define VITAL start as cost-effective if its ICER is < 50% of Malawi GDP ( $0.5 \times \$250 = \$125/\text{YLS}$ ), compared to standard pre-ART counseling. We will also consider alternative thresholds of 100% and 300% of GDP.

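### The cost-effectiveness ratio uses the 6-month effect only, although the trial is judged at month 12 and viral load is measured then too; a month-12 ratio is a cheap improvement

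*Combined protocol and SAP*

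**What the plan says.** Under Specific aim 3, the cost effectiveness analysis paragraph takes as the ICER's effect the "primary outcome of economic interest: proportion of women virally suppressed at 6 months follow up". Aim 3, as worded in the objectives and repeated above the costing text, gives no time point.

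The effectiveness side is set later. The data analysis plan states: "The primary efficacy endpoint is the composite outcome of achievement of retention and viral suppression at Month 12". The sample size and outcome measures sections also work to 12 months. The month-6 result ranks lower: "Secondary efficacy outcomes include achievement of retention and viral load suppression at month 6". Data exist at both times, since the follow-up paragraph says: "Dried blood spots for viral load (VL) testing will be collected at 6- and 12 months".

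The decision rule reads: "we will define VITAL start as cost-effective if its ICER is < 50% of Malawi GDP", worked out in the text as $125 per YLS. One-way and multi-way sensitivity analyses cover conditions "such as lower pricing of video production, mode of delivery, tablets, and alternate health care workers cadres to deliver the intervention", followed by a bootstrap. No 12-month ICER and no durability scenario is named, and no reason for month 6 is given.

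**The concern.** VITAL start is one session of about 37 minutes meant to support lifelong treatment, so its value depends on whether its effect lasts. The plan measures the effect at month 12, makes that the test of the intervention, and then does its economics on the earlier, secondary time point.

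The planned analyses do not close the gap. The named sensitivity inputs concern cost and delivery. Bootstrapping month-6 data describes sampling uncertainty in the month-6 effect and cannot show what had happened by month 12. A favourable ICER could therefore stand beside a null month-12 result, or an unfavourable one beside a positive result, from the same women. The Ministry of Health, named as the main implementer, would have no month-12 ratio with which to reconcile them.

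**Working it through.** **The plan's own figure.** 0.5 × $250 = $125, which reproduces. It is per YLS, whereas the ICER is per additional woman suppressed. No conversion is described, so the working below concerns the ratio and not a verdict against $125.

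**How the ICER depends on the time point.** Let C be the incremental cost per woman, and d6 and d12 the between-arm differences in the proportion suppressed. The costing covers the video and the counselling session, so C is the same at either time.

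- ICER6 = C / d6 and ICER12 = C / d12.
- Hence, for C > 0 and positive differences, ICER12 = ICER6 × (d6 / d12).
- For any limit L per additional woman suppressed, the verdict is favourable at month 6 if C < L × d6 and at month 12 if C < L × d12. The two verdicts differ only if C lies between these values.
- If C ≤ 0, any positive difference gives a favourable verdict at either time.

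**Overall retention between the two times.** The Background section gives: "The most recent Malawi national B+ retention rates were 78%, 71%, and 67% at 6, 12, and 24 months, respectively". From the counts in Table 1:

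| Clinic | 6 months | 12 months |
|---|---|---|
| Kawale | 256/377 = 67.9% | 230/406 = 56.7% |
| Area 25 | 249/401 = 62.1% | 206/385 = 53.5% (printed 58%) |
| Mangochi | 51/112 = 45.5% | 64/121 = 52.9% |
| Salima | 215/269 = 79.9% | 197/269 = 73.2% |

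Pooling the three sites named under Study Clinics (Kawale, Area 25, Mangochi): (256 + 249 + 51)/(377 + 401 + 112) = 556/890 = 62.5% at 6 months, and (230 + 206 + 64)/(406 + 385 + 121) = 500/912 = 54.8% at 12 months.

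Loss therefore continues nationally and in the pooled figures, but not at Mangochi. The denominators differ at every clinic except Salima, so these are mostly not one cohort followed over time. All are single-group figures from routine care and contain no between-arm difference.

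**What the multiplier d6/d12 could be.** Every scenario is an assumption. The first and third start from 15 points, the design difference ("A difference of 15% was selected as the smallest difference that would be of clinical significance").

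- *Difference shrinks in proportion to national retention.* d12 = 15 × 71/78 = 13.7 points; multiplier 78/71 = 1.10. The printed clinic percentages give 68/57 = 1.19 (Kawale), 80/73 = 1.10 (Salima), 62/58 = 1.07 (Area 25; 62.1/53.5 = 1.16 from its counts) and 46/53 = 0.87 (Mangochi).
- *Difference widens.* Take the national figures as the control arm and a constant hazard ratio of 0.6 for loss from care, looking at retention only. d6 = 0.78^0.6 − 0.78 = 0.0815 (8.2 points); d12 = 0.71^0.6 − 0.71 = 0.1042 (10.4 points). Multiplier 0.0815/0.1042 = 0.78, so the 12-month ICER is about 22% lower.
- *Difference halves.* 15 to 7.5 points; multiplier 2. Nothing in the documents supports this particular fall.
- *Difference vanishes.* No finite 12-month ICER exists, while the 6-month ICER would still be reported.

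**Sign of C.** The video session takes about 37 minutes and the flipchart session typically one hour, a saving of about 60 − 37 = 23 minutes of counselling. Against that stand video production and tablets. The documents give no cost totals, so the sign of C is unknown.

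**The case against.** A reader might infer from the retention figures that the benefit will have faded by month 12, so that the plan would call a vanished effect cost-effective. The documents do not support that. Falling retention in one group says nothing about the difference between two, and the hazard-ratio example shows continuing loss going with a growing difference.

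Further points on the other side carry some weight:

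- Month 6 may not be arbitrary. Costing takes the Ministry's perspective, and Table 2 schedules routine viral load testing at 6 months and then at 2 years. The protocol does not give this as its reason, and the study collects its own month-12 sample.
- Month-12 retention, suppression and their composite are all reported under Aim 1, so a null result would be visible. That is true, but it would not be carried into the ICER.
- The sensitivity list is introduced as examples and is not exhaustive. A time-point scenario is possible, but none is stated.
- The $125 limit is per YLS, so no verdict follows directly from the ratio at either time. This stands as a separate gap. Any conversion from suppression to life-years would need an assumption about how long suppression lasts, which makes the later measurement more useful.
- Replacing an economic outcome after enrolment could look post hoc. This is fair, and it is why the 6-month ICER should be kept.

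**Conclusion.** The mismatch is real: the ICER is tied to month 6, the trial is judged at month 12, data exist at both times, and neither a reason nor a check on durability is given. It is best classed as a cheap improvement to a secondary aim. The primary efficacy analysis is untouched.

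Its size cannot be fixed from the documents, which give neither costs nor between-arm results. If the difference only tracks overall retention, the ICER moves modestly: about 10% upward on national figures, and between 13% lower and 19% higher across the printed clinic percentages. A larger move in either direction needs a real change in the between-arm difference. A changed verdict also needs a positive incremental cost and an ICER near the limit, unless the effect vanishes or reverses. If the intervention costs no more than the flipchart session, a smaller but still positive effect changes nothing.

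**What to change.** In the cost effectiveness analysis paragraph of Specific aim 3:

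- Calculate the base-case ICER with the month-12 effect as defined for the primary endpoint (retained and viral load below 1000 copies/ml).
- Use that effect in the bootstrap and in the one-way and multi-way sensitivity analyses.
- Keep the 6-month ICER now specified, report it alongside, and label it as the prespecified one.
- Record the change, its date and its reason, because the sample size section already reports 800 participants enrolled.

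The cost is a few sentences and a small amount of extra analysis, with no new data collection. There are two drawbacks. The composite counts transfers out, and missing viral loads, as failures, so the new base case differs from the current one in definition as well as in time; the month-6 composite, already a secondary outcome, would allow a like-for-like comparison. The ICER may also prove less favourable, or more favourable, than at month 6.
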